9.2.1. Inclusion criteria

Patients must meet all of the following inclusion criteria to be eligible for inclusion in the study:

[figure not shown]
1. Be of legal age (>18 years).
2. Have participated in studies B3461028 and/or B3461045 in Spain.
3. Have been treated for at least 12 months with tafamidis free acid 61 mg.
4. Have a minimum of 12 months of neurological follow-up after starting treatment with tafamidis free acid 61 mg and have data from previous neurological evaluation or at the time of starting treatment with tafamidis free acid 61 mg.
5. Have been diagnosed with ATTR amyloidosis polyneuropathy (ATTR-PN), based on any of the following criteria:
 - a. Decreased amplitude in EMG studies, at least two nerves below normal, excluding median, or other nerve entrapment sites.
 - b. A reduction in amplitude by more than 50% by at least two nerves above the patient's baseline value, excluding the median.
 - c. Two different altered fine fiber tests (Sudoscan, CRS, RR interval variability, skin biopsy...).
 - d. A clinic compatible with small fiber neuropathy (painful or dysautonomic) and an altered fine fiber test.

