4.1 Inclusion Criteria

Patients must meet all of the following inclusion criteria to be eligible for this study:

1. Be of legal age (>18 years).
2. Have participated in studies B3461028 and/or B3461045 in Spain.
3. Have been treated for at least 12 months with Tafamidis free acid 61 mg.
4. Have a minimum of 12 months of neurological follow-up after starting treatment with Tafamidis free acid 61 mg and have data from previous neurological evaluation or at the time of starting treatment with Tafamidis free acid 61 mg.
5. Have been diagnosed with ATTR amyloidosis polyneuropathy (ATTR-PN), based on any of the following criteria:
 - a. Decreased amplitude in EMG studies, at least two nerves below normal, excluding median, or other nerve entrapment sites.
 - b. A reduction in amplitude by more than 50% by at least two nerves above the patient's baseline value, excluding the median.
 - c. Two different altered fine fiber tests (Sudoscan, CRS, RR interval variability, skin biopsy, etc.).
 - d. A clinical picture consistent with small fiber neuropathy (painful or dysautonomic) and an altered fine fiber test.

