5 POPULATION TO BE ANALYZED

The patient's classification is defined below based on compliance with the screening criteria:

- ***Evaluable patients*** are defined as those who meet all of the inclusion criteria and none of the exclusion criteria described in the protocol.
- ***Non-evaluable patients*** are defined as those who fail to meet any of the inclusion criteria or meet one or more exclusion criteria.

Information regarding the screening criteria in the form of a binary variable (Yes / No) is recorded on the CRF for each item described.

Several of these criteria can be checked against the data collected in the CRF. The criteria that will be verified in order to define the evaluable population are described below:

Inclusion Criteria

Patients must meet all of the following inclusion criteria to be eligible for this study:

1. *Be of legal age (>18 years).*

Age of all patients at enrollment will be checked to ensure they are 18 years old or above.

2. *Have participated in studies B3461028 and/or B3461045 in Spain.*

A check will be carried out to ensure patients have answered 'yes' to one of the following questions:

- Has the patient participated in study B3461028?
- Has the patient participated in study B3461045?

It will also be confirmed that they have collected the date of the consent indicated for the corresponding previous study.

3. Have been treated for at least 12 months with Tafamidis free acid 61 mg.

The difference between the Tafamidis 61 mg end date minus its start date will be checked to ensure it is at least 12 months, or otherwise the Tafamidis 80 mg end date minus its start date is at least 12 months:

(End date* - start date* \geq 12 months)

*Dates for Tafamidis 61 mg or 80 mg

In such cases where they are on treatment with Tafamidis 61 mg, the date of inclusion in this study will be considered as “End Date”.

4. Have a minimum of 12 months of neurological follow-up after starting treatment with Tafamidis free acid 61 mg and have data from previous neurological evaluation or at the time of starting treatment with Tafamidis free acid 61 mg.

For all patients, the difference between the last follow-up and the start of treatment with Tafamidis (61 or 80 mg) will be checked to ensure it is at least 12 months.

(Last follow-up date - treatment start date* \geq 12 months)

*The first date of treatment with Tafamidis 61 mg or 80 mg

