A check will be carried out to ensure that data is available for all patients in the following neurological variables, in the 12 months prior to inclusion in the studies (B3461028 and/or LTE B3461045) or at inclusion in the same studies (start of treatment with Tafamidis 61 mg):

- NIS (Neuropathy Impairment Score)
- NIS-LL (Neuropathy Impairment Score Lower Limbs)
- FAP (Familial Amyloidotic Polyneuropathy stage)
- PND (Polyneuropathy Disability Score)

5. *Have been diagnosed with ATTR amyloidosis polyneuropathy (ATTR-PN), based on any of the following criteria:*

- a. **Decreased amplitude in EMG studies, at least two nerves below normal, excluding median, or other nerve entrapment sites.**
- b. **A reduction in amplitude by more than 50% by at least two nerves above the patient's baseline value, excluding the median.**
- c. **Two different altered fine fiber tests (Sudoscan, CRS, RR interval variability, skin biopsy, etc.).**
- d. **A clinical picture consistent with small fiber neuropathy (painful or dysautonomic) and an altered fine fiber test.**

This inclusion criterion cannot be confirmed with the data collected in the CRF, so only the information collected in the yes/no variable of the screening criteria is considered.

A check will be carried out to ensure that the genotype (Mutation / Wild type) has been indicated for all patients.

Exclusion criteria

Patients who meet any of the following criteria will not be included in the study:

1. ***Treatment with Tafamidis free acid 61 mg for less than 12 months.***

In this section, refer to the inclusion criterion 3 check.

2. ***Not having a minimum of 12 months of neurological follow-up after starting treatment with Tafamidis free acid 61 mg.***

In this section, refer to the inclusion criterion 4 check.

3. ***Etiological diagnosis of polyneuropathy other than ATTR.***

No check with CRF.

Analyses will be performed with evaluable patients on the total population and subgroup based on genotype (ATTRv and ATTRwt).

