6.1 Visit reassignment

6.1.1 Numerical variables at follow-up (neurological and scales)

In the section on variables in follow-up, there are visit dates and no months assigned to those visits. To avoid time variability and ensure consistency of the data, for each quantitative follow-up variable, the following procedure will be calculated. All values will be assigned, as of the follow-up date, weighing the assignments based on the recorded follow-ups.

1. Months between visits:

Firstly, the date difference between the first follow-up and the start time will be calculated for the variable in question. Values will be assigned to those visits that are close to this difference or lower, i.e. if the difference is 25 months, visits up to Month 24 will be allocated (see note 3 below).

2. Monthly unit change (exchange rate):

$$\frac{(\text{value at follow-up visit} - \text{value at start of treatment visit})}{\text{months between visits}}$$

3. Increment for each visit:

Monthly unit change x 6

Monthly unit change x 12

Monthly unit change x 18

Monthly unit change x 24

Monthly unit change x 36

4. Value assigned at each visit:

Baseline value + Increment for each visit

NOTE 3:

- In case only one follow-up is available and the total follow-ups cannot be assigned, the “last value carried forward” (LVCF) method will be used, so the last value obtained will be carried over to the end.
- If more than one follow-up is available and the difference between their dates is:
 - Less than 5 months, the value will not be allocated, as the two visits would be very close to each other.
 - Greater than 5 months and less than 10 months, the value of that follow-up will be assigned to the next follow-up pending assignment. That is, if the assignment of the first follow-up

reaches month 24, the assignment of month 36 would be considered as the value recorded in the second follow-up.

– Otherwise, if the difference is greater than 10 months, the values will be assigned with the algorithm from step 1 taking the previous follow-up as baseline.

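### The 12-month follow-up check in SAP 5 does not test for a neurological assessment or an NIS, so a single NIS taken before Month 12 can be carried forward into the primary endpoint

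*SAP*

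**What the plan says.** Protocol 9.2.1, criterion 4, reads "Have a minimum of 12 months of neurological follow-up after starting treatment with tafamidis free acid 61 mg". SAP 4.1 repeats it, and exclusion criterion 2 is its mirror image.

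SAP 5 turns the criterion into a date test: "the difference between the last follow-up and the start of treatment with Tafamidis (61 or 80 mg) will be checked", with the formula "Last follow-up date - treatment start date" required to be at least 12 months. For exclusion 2 it adds no further test: "In this section, refer to the inclusion criterion 4 check". The one place where SAP 5 verifies that NIS exists, together with NIS-LL, FAP and PND, concerns baseline: "in the 12 months prior to inclusion in the studies (B3461028 and/or LTE B3461045) or at inclusion in the same studies". Separately, "Information regarding the screening criteria in the form of a binary variable (Yes / No) is recorded on the CRF for each item described".

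SAP 6.1.1 builds the Month 6 to 36 values separately for each variable from its own follow-up dates. When only one follow-up exists and the later months cannot be filled, NOTE 3 applies last value carried forward, "so the last value obtained will be carried over to the end". SAP 12.1 sends the primary objective to the Month-12 result of SAP 10.3.1 and adds a responder definition of a change below 4 points.

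**The concern.** Criterion 4 should ensure that a 12-month neurological outcome can be observed, but the test written for it can be met by a visit at which no NIS was recorded. The data are retrospective. Protocol 9.3 has routine visits that also carry mBMI, renal and eye data, and Protocol 9.9 lists scarce follow-up data as a limitation. The date of the last NIS can therefore be earlier than the date of the last follow-up.

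At stake is the primary variable. In a patient who is worsening, a value taken before Month 12 and entered as Month 12 understates the change. The study has no control group in which the same error would also occur.

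**Working it through.** The documents contain no power or precision calculation to reproduce. The check sets the rules side by side, then follows a patient through SAP 6.1.1.

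**1. What is verified**
- Criterion (Protocol 9.2.1, SAP 4.1): 12 months of neurological follow-up.
- Test (SAP 5): last follow-up minus treatment start, with no neurological qualifier.
- NIS availability (SAP 5): baseline only. No post-baseline NIS is required.

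**2. How Month 12 is filled when NIS stops early**

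The SAP's own example is reproduced first: a first follow-up at 25 months fills Months 6, 12, 18 and 24. The SAP allocates months near or below the elapsed time but gives no window for near, so 0, 1 and 2 months were tried as assumptions.
- One follow-up NIS, at any month from 3 to 11: with 0 months, Month 12 is always carried forward. With 1 month, an NIS at month 11 is extrapolated instead. With 2 months, an NIS at month 10 or 11 is extrapolated. Month 7 is carried forward under all three readings.
- Two follow-up NIS, both before Month 12 (55 whole-month pairs): carry-forward never applies. Month 12 is unassigned in 55, 54 and 51 of the 55 pairs respectively. Seven of the unassigned pairs have a gap of exactly 5 or 10 months, which NOTE 3 does not cover. The few others get a shifted or extrapolated value. Off whole months, NIS at 6 and 11.5 months would place the 11.5-month value at Month 12.

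**3. Which rule governs the single-NIS patient**

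Assume linear worsening at 0.5 points per month and one NIS at month 7. The Month-12 change is then:
- NOTE 3, observed value carried: 7 × 0.5 = +3.5, responder.
- NOTE 3, if the value carried is the one assigned to Month 6: 6 × 0.5 = +3.0, responder.
- SAP 10.3.1, change equals the reassignment increment: 12 × 0.5 = +6.0, non-responder. The SAP does not say what this increment is for a carried value.
- SAP 6 (no imputation) and SAP 12.1 (incomplete responder data left missing): missing.

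The SAP does not say which prevails.

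**4. Size if NOTE 3 prevails**
- Carried change = rate × t, where t is the month of the only follow-up NIS; linear 12-month change = rate × 12.
- With t = 7, the class flips when rate × 12 ≥ 4 and rate × 7 < 4, that is from 4/12 = 0.33 up to 4/7 = 0.57 points per month.
- In general, a carried change below 4 corresponds to a 12-month change below 4 × 12/t: 8.0 for t = 6, 6.0 for t = 8, 5.33 for t = 9.
- With the 10 ATTRv patients estimated in SAP 4, one reclassified patient is 1/10 = 10 percentage points. If all ten truly changed by 6.0 and one is entered as 3.5, the mean is (9 × 6.0 + 3.5)/10 = 5.75.

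**The case against.** The date test stands directly under a restatement of criterion 4, so last follow-up can naturally be read as last neurological follow-up. A reader might infer that the SAP deliberately accepts a visit of any kind. It does not say so; the qualifier is only absent. Protocol 9.3 lists NIS among the variables collected at each follow-up visit and describes no separate non-neurological visits. Evaluable patients are defined as those meeting the protocol's criteria, and the CRF holds a Yes/No for each.

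These are real but partial safeguards. The SAP does not say whether the Yes/No or the date test prevails if they disagree. A truthful Yes can also rest on a neurological assessment other than NIS, because criterion 4 does not itself require a 12-month NIS. That last point limits the remedy: an NIS requirement belongs with the endpoint, not with eligibility.

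A reader might also infer that every patient whose NIS stops before Month 12 gets a carried-forward primary value. Step 2 shows otherwise: it takes exactly one follow-up NIS, and one not near Month 12.

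Finally, the harm arises in SAP 6.1.1 rather than in the check itself. This is fair. The check lets the patient in and NOTE 3 supplies the value, so both need attention.

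**Conclusion.** The concern holds in limited form. The SAP 5 check does not verify neurological follow-up, nothing requires a post-baseline NIS, and a patient with a single early NIS can be evaluable and receive a carried-forward Month-12 value. That value contradicts SAP 6 and SAP 12.1, and its change is undefined in SAP 10.3.1.

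The reclassification from +6.0 to +3.5 is an illustration, not an estimate of bias. It rests on an assumed slope, linear worsening, an assumed visit month, n = 10, and NOTE 3 overriding the other three sections. The documents do not show that any patient is affected. It is worth correcting because the error, where it occurs in a worsening patient, favours the drug in a very small uncontrolled study, and the correction is cheap.

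**What to change.** - **SAP 5, criterion 4:** base the check on the date of the last neurological assessment, and state which source prevails if it disagrees with the CRF Yes/No.
- **SAP 10.3.1 and 12.1:** for the Month-12 NIS, require a recorded NIS at or after Month 12, or within a Month-12 window. The SAP has no such window and must state one. Otherwise leave Month-12 NIS missing, in line with SAP 6 and the responder rule of 12.1.
- **SAP 6.1.1, NOTE 3:** exempt Month-12 NIS from carry-forward.
- **Population:** patients without a qualifying NIS stay evaluable for the other analyses if they meet criterion 4, so eligibility is not tightened beyond the protocol.
- **Report:** give the number of Month-12 NIS values that are observed, interpolated, extrapolated or shifted.

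The assessment dates are already recorded, so no new data are needed. The cost is a few edited sentences and possibly a slightly smaller N for the primary endpoint; each ATTRv patient set to missing is one of an estimated 10.

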12 ANALYSIS OF THE OBJECTIVES

12.1 Primary objective

“To determine the efficacy of Tafamidis free acid 61 mg in ATTRv patients with neurologic involvement included in studies B3461045 and/or LTE (B3461045) in Spain through changes in the 12-month NIS scale”

Primary variable: Neuropathy Impairment Score (NIS).

NOTE: ATTRv patients are considered to be those who have indicated “Mutation” in the genotype (Data related to the disease at diagnosis).

See resolution of this objective in 10.3.1 (month 12).

Additionally, the results will be presented for the percentage of patients responding to treatment of the change at month 12 with respect to the initial value. The N and % of patients responding to treatment will be calculated, defining responder as:

- change at 12 months compared to the initial data <4p in NIS, patients who have obtained less than 4 points in the NIS in month 12

Patients who do not meet the previous condition will be considered non-responders. If complete data is not available, the value will be left as missing.

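### SAP 5 checks every patient for baseline NIS, NIS-LL, FAP and PND, although the protocol criterion names no scale, so a patient with complete NIS data can drop out of the primary NIS analysis

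*SAP*

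**What the plan says.** Protocol 9.2.1, criterion 4, requires 12 months of neurological follow-up and that patients "have data from previous neurological evaluation or at the time of starting treatment with tafamidis free acid 61 mg". SAP 4.1 repeats the requirement. Neither names an instrument.

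SAP 5 defines evaluable patients as "those who meet all of the inclusion criteria and none of the exclusion criteria described in the protocol", and non-evaluable patients as "those who fail to meet any of the inclusion criteria or meet one or more exclusion criteria". It introduces its list of checks with "The criteria that will be verified in order to define the evaluable population are described below". For criterion 4 the check reads "A check will be carried out to ensure that data is available for all patients in the following neurological variables", covering the 12 months before inclusion in the parent studies or inclusion itself. The list under it is NIS, NIS-LL, FAP and PND. The section closes by restricting analyses to evaluable patients, overall and by genotype.

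SAP 12.1 names NIS as the only primary variable. The analysis is the Month-12 change in ATTRv patients, with a responder percentage based on a NIS change below 4 points. SAP 6 leaves missing values unimputed and gives N for each quantitative variable.

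**The concern.** The check is narrower than the criterion it implements. A gap in a scale that the primary analysis does not use could remove a patient from every analysis, including the primary one. SAP 4 expects only 10 ATTRv patients, so each loss is noticeable.

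The SAP also disagrees with itself. It defines evaluable by the protocol's criteria and then verifies something stricter. Two programmers working from the same text could build different analysis sets.

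**Working it through.** **No plan figure to reproduce.** The 10 ATTRv and 10 ATTRwt patients in SAP 4 are a feasibility count. No alpha, power, effect size or SD stands behind them. The main check is therefore to apply the texts to one patient.

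**One patient, four texts.** Take an ATTRv patient with baseline and Month-12 NIS, no baseline FAP stage recorded, and every other criterion met.

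| Text | Result |
|---|---|
| Protocol 9.2.1 and SAP 4.1, criterion 4 | Met: a baseline neurological evaluation exists |
| SAP 5, definition of evaluable (refers to the protocol) | Evaluable |
| SAP 5, check for criterion 4, as written | Fails: one of the four listed variables is absent |
| SAP 12.1, data needed for the primary analysis | Complete: NIS at both times |

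The same holds if NIS-LL or PND is the missing item. Requiring baseline NIS costs the primary analysis nothing, because no change can be calculated without it. The excess lies in the other three.

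**Is the list meant as alternatives?** Nothing says so. In the same section, the check for criterion 2 accepts a yes to either of two questions, and criterion 5 accepts any one of its sub-criteria. The four-scale list has no such wording.

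**Illustrative size of the loss.** The missing rate is not in the documents. Assume that each extra item is missing in a share m of patients who have NIS, with m from 5% to 20%, and that k items are missing independently. If all items are always missing together, k = 1.

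- Share lost: p = 1 − (1 − m)^k
- Expected loss among 10: 10p
- Chance of losing at least one: 1 − (1 − p)^10

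| Case | m = 5% | m = 10% | m = 20% |
|---|---|---|---|
| k = 1 | 0.5 lost; 40% | 1.0; 65% | 2.0; 89% |
| k = 2 (FAP, PND) | 1.0; 64% | 1.9; 88% | 3.6; 99% |
| k = 3 (plus NIS-LL) | 1.4; 79% | 2.7; 96% | 4.9; 99.9% |

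Each cell gives the expected number lost of 10, then the chance of losing at least one.

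**Consequence for precision.** The half-width of a t-based 95% confidence interval for a mean, in SD units, is t(0.975, n − 1)/√n.

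- n = 10: 0.715; one patient = 100/10 = 10 percentage points of the responder rate
- n = 8: 0.836; one patient = 100/8 = 12.5 points
- Ratio: 0.836/0.715 = 1.17, so 17% wider

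**The case against.** The strongest reply is that this is a data-completeness check and not an exclusion rule.

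- Evaluable is defined by the protocol's criteria, and the SAP states no consequence for failing the four-scale check.
- Almost the same phrase is used for genotype, whose recording is not an inclusion criterion. The confirmation of the parent-study consent date is similar.
- Protocol 9.8 provides for queries on key missing variables, to be resolved before the database closes.
- Protocol 9.3 lets PND be calculated from the record. The FAP and PND categories rest largely on walking ability, and NIS-LL covers the same domains as NIS in the lower limbs. A patient with NIS but without the others may be rare.
- SAP 5.1 would show any non-evaluable patient with the reason.
- SAP 6 lists no confidence interval among its summaries.

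Much of this stands. The lenient reading is possible, the number affected may be zero, and the interval width is only a yardstick for lost information. But no text writes the lenient reading, and SAP 5 says in terms that the checks define the analysis set. Displaying an exclusion does not prevent it. The list of key variables for queries is not shown, so it cannot be assumed that these three items will be queried.

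A reader might go further in four ways that the documents do not support:

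- **That baseline stages are known to be sparse.** Protocol 9.9 warns of scarce data at follow-up visits, not at baseline.
- **That the check selects patients from sites with fuller neurological work-up.** Nothing in the documents shows this.
- **That reading the list as any one of the four would also harm the primary analysis.** A patient without baseline NIS would simply be missing for NIS under SAP 6 and could still contribute to other scales.
- **That the other scales are irrelevant to the study.** All four are outcomes in Protocol 9.1. The point is only that three of them are not needed for the primary one.

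**Conclusion.** The mismatch is real and rests on the text alone: the check is stricter than the protocol criterion and conflicts with the SAP's own definition of evaluable. On the plain reading, an ATTRv patient with complete NIS data can be excluded from the primary analysis for lack of a baseline NIS-LL, FAP or PND. It is not shown that any patient will be.

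The size of the loss is wholly assumed. The move from 10 to 8 patients shows only what a loss of two would cost. Because the expected set is so small and the correction is short, the wording should be settled before the evaluable set is fixed.

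**What to change.** In SAP 5, criterion 4, replace the four-scale check with wording to this effect: a patient meets the baseline part of the criterion if any neurological evaluation is available before or at the start of 61 mg, as in the protocol; a missing NIS-LL, FAP or PND does not make a patient non-evaluable; the primary analysis uses evaluable ATTRv patients with a baseline NIS; every other scale is treated as missing per variable under SAP 6, with N reported per scale.

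The four-scale review can remain as a data query, labelled as such, with a count of patients lacking each item.

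The cost is a few lines in the SAP and no new data. The downside is that N will differ between endpoints, but the planned tables already report N for each variable.
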